#### **14.9.9 Data Evaluation**

Recovery for each of the samples will be expressed as  $\log_{10}$  CFU/mL.

Neutralizer Effectiveness:

If the mean  $\log_{10}$  CFU/mL of the sample is not more than 0.3  $\log_{10}$  less than the mean  $\log_{10}$  CFU/mL of the NC, the neutralization will be considered effective.

- Mean  $\log_{10}$  CFU/mL from NC – Mean  $\log_{10}$  CFU/mL from sample (use corresponding time points)

Neutralizer Toxicity:

If the mean  $\log_{10}$  CFU/mL of the TC is not more than 0.3  $\log_{10}$  less than the mean  $\log_{10}$  CFU/mL of the NC, the sampling solutions will be considered non-toxic.

- Mean  $\log_{10}$  CFU/mL from NC – Mean  $\log_{10}$  CFU/mL from TC (use corresponding time points).

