#### 6.2 Assessment Methods

##### 6.2.1 Microbiological Methods

###### 6.2.1.1 Sample Collection and Processing

Quantitative cultures will be obtained from sampling sites using a modification of the cup scrub method of Williamson and Kligman.

[REDACTED]

A sterile scrub cup will be placed and held firmly on each site. **Scrub 1:** [REDACTED] [REDACTED] SSS will be aseptically pipetted into the scrub cup. The skin will be scrubbed in a circular motion with moderate pressure for 1 minute using a sterile policeman. Using a sterile transfer pipette, the scrub solution will be transferred to a sterile collection tube. **Scrub 2:** [REDACTED] [REDACTED] fresh SSS will be pipetted into the scrub cup and the scrub procedure will be [REDACTED]

[REDACTED]

repeated. This solution will be pooled with the solution from Scrub 1 for a total sample volume of approximately 6 mL per site.

Following collection, each sample tube will be capped tightly [REDACTED] followed by [REDACTED] 30-second vortex. A 1.0 mL aliquot of each sample will be diluted into sterile tubes containing 9.0 mL PBW. Serial 10-fold dilutions will be performed in PBW, as appropriate. One-milliliter (1.0-mL) aliquots of selected dilutions will be pour-plated in duplicate using TSA+N. **Samples must be plated within 30 minutes of collection.** [REDACTED] After 72 [REDACTED] hours of aerobic incubation at  $30 \pm 2^{\circ}\text{C}$ , colonies will be counted and viable cells in the original sample will be calculated using standard methods. [REDACTED]

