##### Numbers Control (NC):

Add 100  $\mu\text{L}$  of the appropriate diluted inoculum to a tube containing 5 mL PBW to yield final inoculum concentrations of ~20-200 CFU/mL. [REDACTED]

[REDACTED] Pour-plate triplicate [REDACTED] aliquots immediately (<1 minute) and [REDACTED] minutes [REDACTED] post-inoculation in the same manner as 14.9.7.2, except using TSA without neutralizers.

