##### Toxicity Control (TC-MSS):

Add [REDACTED] 5.0 mL SSS [REDACTED]

[REDACTED] to a clean tube. Add 100  $\mu\text{L}$  of the appropriate diluted inoculum to the 5-mL tube to yield final inoculum concentrations of ~20-200 CFU/mL. Pour-plate triplicate [REDACTED] aliquots immediately (<1 minute) and [REDACTED] minutes [REDACTED] post-inoculation in the same manner as 14.9.7.2.

These controls will provide assurance that the test organisms are not adversely affected by the treatments or the sampling procedures.

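### Neutralizer effectiveness is judged only against a control in a different fluid and agar; adding the matched contrast (TC minus sample) would close an uncapped route for residual kill

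*Combined protocol and SAP*

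**What the plan says.** The neutralization validation in Appendix 14.9 involves three preparations.

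- **Sample.** Scrub fluid from treated abdominal skin, collected as in Section 6.2.1.1 (so in SSS), then inoculated and plated on TSA+N (14.9.7.2).
- **Numbers Control (NC).** 100 µL "of the appropriate diluted inoculum to a tube containing 5 mL PBW", then plated "in the same manner as 14.9.7.2, except using TSA without neutralizers".
- **Toxicity Control (TC).** The same inoculum in 5.0 mL SSS, plated as in 14.9.7.2 and therefore on TSA+N. Some text around the NC and TC preparation is redacted.

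All three are plated immediately and at a second, redacted time point. Section 14.9.9 then plans two one-sided contrasts at corresponding time points. For effectiveness, if the mean log10 CFU/mL "of the sample is not more than 0.3" log10 below the mean log10 "CFU/mL of the NC, the neutralization will be considered effective". For toxicity, the same limit applies to the TC: if it is met relative to the mean log10 "CFU/mL of the NC, the sampling solutions will be considered non-toxic". No contrast of TC with sample is listed.

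In the trial itself, one method serves baseline and post-prep samples: SSS cup scrubs whose "aliquots of selected dilutions will be pour-plated in duplicate using TSA+N" (6.2.1.1).

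**The concern.** The effectiveness contrast changes three things at once: exposure to the product, the fluid and the agar. A shortfall in the sample may come from product still acting, or from SSS and TSA+N supporting growth differently from PBW and plain TSA. The two can also offset each other. If SSS/TSA+N recovers more organisms than PBW/TSA, or if organisms decline in PBW by the second time point, the NC sits low and hides residual kill.

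The control that removes most of this ambiguity is already being run. The TC matches the sample in fluid and agar, so TC minus sample lies closer to the bias that would enter the trial, where baseline and post-prep samples share SSS and TSA+N and a common fluid or agar effect largely cancels.

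Section 14.9.1 itself says that inadequate neutralization leads antimicrobial activity to be overestimated. The coverage decision in 8.2.1 is a mean log10 reduction of 2.0 at all three locations, so the error would run in the favourable direction against a fixed threshold.

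**Working it through.** **Inputs from the documents.** Limit of 0.3 log10 for both rules, and NC as comparator in both (14.9.9). Six subjects (14.9.3) with two samples each, one per inoculum (14.9.7.2), hence six samples per inoculum. Controls in triplicate (14.9.7.3). Efficacy threshold 2.0 (8.2.1). The 0.3 limit is a fixed criterion with no derivation, so there is no calculation to reproduce.

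**Assumptions.** The documents give neither TC minus NC nor a replicate SD. Both are varied or stated below.

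**Step 1: decomposition.** Write d = TC − NC and r = TC − sample (residual kill in the matched fluid and agar). Then

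NC − sample = (NC − TC) + (TC − sample) = r − d.

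The effectiveness rule, r − d ≤ 0.3, passes any r up to 0.3 + d. The toxicity rule requires only −d ≤ 0.3, so it puts no upper limit on d.

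**Step 2: largest residual kill that passes in expectation.** Share killed = 1 − 10^(−r). The last column is 2.0 − r and supposes that the validation loss carries over in full.

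| Assumed TC − NC | Largest r passed | Share killed | True mean if 2.0 is observed |
|---|---|---|---|
| −0.2 | 0.1 | 21% | 1.9 |
| −0.1 | 0.2 | 37% | 1.8 |
| 0 | 0.3 | 50% | 1.7 |
| +0.1 | 0.4 | 60% | 1.6 |
| +0.2 | 0.5 | 68% | 1.5 |

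A matched rule would hold r at 0.3 in every row. The excess over the intended limit is therefore 0.1 or 0.2 log10 in the last two rows, and there is none in the others.

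**Step 3: chance of passing, for one organism and time point.** Assume a replicate SD of 0.15 log10. SE = √(0.15²/6 + 0.15²/3) = 0.106.

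- d = +0.2, r = 0.45. NC rule: Φ((0.30 − 0.25)/0.106) = 68%. TC rule: Φ((0.30 − 0.45)/0.106) = 8%.
- d = −0.1, r = 0.35. NC rule: Φ((0.30 − 0.45)/0.106) = 8%. TC rule: Φ((0.30 − 0.35)/0.106) = 32%.

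A simulation with Poisson plate counts (mean 20 to 196 per plate, between-tube SD 0.05 or 0.10, three plates per tube) agrees in direction. At d = +0.2 and r = 0.40, the NC rule passed 88–100% of runs and the TC rule 0.5–10%. At d = 0 and r = 0.40, both passed 0.4–11%.

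**Step 4: what a third criterion would add.** In the observed means, TC − sample = (NC − sample) − (NC − TC). If the observed TC is at or below the observed NC, passing the present effectiveness rule already forces TC − sample ≤ 0.3. The added criterion can change the result only when the observed TC exceeds the NC. With complete neutralization (r = 0) and SD 0.15, it would fail by chance with probability 1 − Φ(0.30/0.106) = 0.2%; with r = 0.1, 1 − Φ(0.20/0.106) = 3%. These are upper bounds on the extra failures per organism and time point.

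**The case against.** The strongest reply is that the harmful direction has no support in the documents. They raise only the opposite worry, that neutralizers might be toxic; TC would then lie below NC and the current rule would be the stricter one. NC minus sample is also a coherent joint check of the two requirements in 14.9.1, no effect on growth and inactivation of the product. This stands. It means the size is unknown, and it means the NC criterion should not be replaced: at TC 0.1 below NC and a loss of 0.35, replacement would raise the pass rate from 8% to 32%.

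There are partial safeguards. Inoculum density is verified at the beginning and end (14.9.7.1), and the NC is plated at both time points, so a decline in PBW would be visible. At under one minute there is little time for one. But no rule in 14.9.9 acts on what is seen.

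The TC is not a perfect match. It has had no skin contact, and trial samples are serially diluted in PBW before plating, so a fluid effect need not cancel fully. Moving a loss measured on the abdomen at low inoculum to the back is a further step. These points limit how literally the last column of the table can be read.

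The validation is based on ASTM E1054, which is not available here; whether it prescribes the comparator cannot be checked.

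A reader might also infer that the rule wrongly fails sound systems. The documents do not support that as a material problem. A system with no residual kill that truly meets the toxicity limit has an expected NC minus sample of at most 0.3, so it fails only through sampling error. Near that boundary the toxicity rule itself fails often, and such failures are conservative for efficacy.

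**Conclusion.** The point holds as a minor improvement. The mismatch in fluid and agar is plain in the text, the matched contrast is not planned, and nothing limits TC above NC. The residual kill that can pass is 0.3 + (TC minus NC) log10, so 0.4 or 0.5 for assumed differences of +0.1 or +0.2. If the controls agree, or TC is lower, nothing is lost. The pass rates rest on an assumed SD and illustrate the mechanism only.

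It would be tempting to conclude that the trial's reductions are inflated, or that an observed 2.0 is really 1.5. The documents do not show this: they give no TC minus NC value and no measured residual loss, and how fully an abdominal validation loss would carry over to the back is unknown. The statement in 14.9.7.3, "These controls will provide assurance that the test organisms are not adversely affected by the treatments or the sampling procedures", is reasonable for toxicity. What is missing is the use of the same TC plates to isolate residual product activity.

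**What to change.** In 14.9.9, add a required criterion: mean log10 CFU/mL of TC minus mean log10 CFU/mL of sample is not more than 0.3, for each organism at each corresponding time point. Keep both existing criteria, NC minus sample and NC minus TC, unchanged. Make the change before the validation results are judged; Section 6.2.1.3 places that work before Treatment Day.

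The cost is a line of text. The TC plates are already poured at the same time points, so no laboratory work is added. The downside is a slightly higher chance that the validation fails, confined to cases where the observed TC exceeds the NC.
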